7.5 Treatment Exposure

Treatment exposure will be summarised descriptively by treatment group (placebo, Dysport 600 U, Dysport 800 U, All Dysport) in the Safety population. IMP administration data will be listed for the Safety population.

The treatment exposure will be summarised by number and percentage of subjects treated in each treatment cycle (DBPC cycle, Dysport Cycle 1, Dysport Cycle 2, etc), the number of

Statistical Analysis Plan

Version: Final v1.0

September-2018

Ipsen Protocol No. D-FR-52120-223

000000146513

Date of Issue: 21-

Covance Study ID:

Dysport Cycles will be displayed descriptively using summary statistics for the Safety population.

The treatment exposure in weeks will be summarised by treatment group as below:

For overall study (irrespective of number of treatments)

- Total IMP exposure across the study will be calculated as (Last attended visit date in the study – first IMP administration date + 1) / 7. Data will be presented in weeks for placebo, 600 U Dysport, 800 U Dysport, All Dysport groups.
- The number of subjects cumulatively exposed to IMP for at least 12 weeks, 24 weeks, 52 weeks, 78 weeks and 104 weeks will be summarised for placebo, 600 U Dysport, 800 U Dysport and All Dysport groups.
- Total Dysport exposure across the study will be calculated as (Last attended visit date in the study – first Dysport injection date + 1) / 7. Data will be presented in weeks for 600 U, 800 U and All Dysport groups.
- The number of subjects cumulatively exposed to Dysport at least 12 weeks, 24 weeks, 52 weeks, 78 weeks and 104 weeks will be summarised. Data will be presented in weeks for 600 U, 800 U and All Dysport groups

For Dysport Cycles

- The total number of subjects who received 1, 2, 3, ...etc and at least 1, 2, 3...etc Dysport treatments at 600 U, 800 U and All Dysport will be summarised .

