**PAGE 32/139** 

(UTI) due to impaired voiding following BTX-A treatment, which is observed in subjects not performing CIC.

In addition to BTX-A bladder-naive subjects who have never previously received intradetrusor BTX-A for UI, the study will also enrol BTX-A bladder-non-naive subjects, who have previously received intradetrusor BTX-A for NDO. This will reflect real world usage and it has been demonstrated previously that treatment response does not vary significantly following retreatment in subjects treated with intradetrusor BTX-A for UI due to NDO [18]. In order to be eligible for entry into the study, more than 9 months must have elapsed since any previous intradetrusor BTX-A treatment administration.

### 1.7 Placebo Usage During Treatment 1

The use of placebo during the first IMP treatment administration ensures a rigorous, scientifically appropriate study design to assess the efficacy and safety of Dysport® in the treatment of UI due to NDO. The use of placebo is justified because:

- Although UI due to NDO is a symptomatic condition, which can lead to significantly impaired quality of life, it is not life-threatening. Therefore, a single administration of placebo with the opportunity to receive active IMP treatment from as early as 12 weeks later ensures that all subjects have the opportunity to receive the active IMP without prolonged delay. All further study treatment administrations will be active IMP, for up to 2 years post randomisation, ensuring all subjects also have the opportunity to be treated with active IMP multiple times during the study, if required.
- Treatment with BTX-A may be associated with an increased risk of UTIs in an NDO population that is already susceptible to UTIs. In order to accurately estimate the true incidence of UTIs associated with the active IMP, compared to the background incidence and the incidence due to the treatment administration procedure, a placebo group comparison is required.
- OnabotulinumtoxinA, is not authorised or marketed for the treatment of UI due to NDO in all the planned countries where this Dysport® phase 3 program is to be conducted; therefore, its use as an active comparator in these countries would not be appropriate. An objective of this program is to confirm the efficacy of Dysport® in this indication

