2.2 Overall Study Design

This is a Phase III, multicenter, randomised, double-blind, parallel group, placebo controlled study to assess the efficacy and safety of two Dysport doses (600 U and 800 U) administered to the bladder of adult subjects with NDO due to spinal cord injury (SCI) or multiple sclerosis (MS).

The target population is subjects with UI caused by NDO due to either SCI or MS, who have not been adequately managed with oral medication and who routinely require clean intermittent catheterisation (CIC) to manage their bladder function.

The study will include two treatment periods.

- A double-blind placebo controlled (DBPC) treatment, i.e. following Treatment 1 on Day 1 during which subjects receive a single IMP treatment administration of either
 - Dysport 600 U
 - Dysport 800 U
 - Placebo.
- A subsequent double-blind active treatment period, during which subjects can receive multiple active IMP retreatment administrations of either;
 - Dysport 600 U
 - Dysport 800 U.

Subjects who were randomised to receive Dysport at Treatment 1 (600 U or 800 U) will continue to receive the same dose for all subsequent treatments and those who were initially randomised to placebo will receive either 600 U or 800 U, depending on their allocated randomisation sequence (see next section).

The study contains two subsets:

- Urodynamic subset (planned ≥ 200 subjects)
 - o All subjects in this subset must have standardised urodynamics (as described in the Study Specific Urodynamic Manual) during Screening and at Week 6 following each study treatment
 - o Screening standardised urodynamics must confirm the presence of NDO
- Non-Urodynamic subset
 - o All subjects in this subset must have documented urodynamic proven NDO in the 12 months prior to Screening. If not, then urodynamics must be performed per local practice during Screening to confirm the diagnosis of NDO

Statistical Analysis Plan

Version: Final v1.0

September-2018

Ipsen Protocol No. D-FR-52120-223

000000146513

Date of Issue: 21-

Covance Study ID:

o Urodynamics will not be performed in the post-screening period in this subset

Screening

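### The placebo column for total IMP exposure in SAP 7.5 includes time after the switch to Dysport, and the section gives no placebo-only duration

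*SAP*

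**What the plan says.** SAP 7.5 (Treatment Exposure) summarises exposure by treatment group in the Safety population. Under a sub-heading that reads "For overall study (irrespective of number of treatments", it sets out two measures.

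- **Total IMP exposure** runs from the first IMP administration to the last visit attended in the study: "Total IMP exposure across the study will be calculated as (Last attended visit date in the study", from which the first IMP date is then subtracted. The groups are explicit: "Data will be presented in weeks for placebo, 600 U Dysport, 800 U Dysport, All Dysport groups". The threshold counts use the same groups, with subjects "cumulatively exposed to IMP for at least 12 weeks, 24 weeks, 52 weeks, 78 weeks and 104 weeks will be summarised for placebo" and the Dysport groups.
- **Total Dysport exposure** has the same end date but starts at the first Dysport injection, and has no placebo column: "first Dysport injection date + 1) / 7. Data will be presented in weeks for 600 U, 800 U and All Dysport groups".

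The design makes placebo a single administration. Protocol 1.7 states: "All further study treatment administrations will be active IMP, for up to 2 years post randomisation". SAP 2.2 says the same of the sequences: "those who were initially randomised to placebo will receive either 600 U or 800 U". SAP 7.5 contains no rule that stops placebo time at the first Dysport injection.

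**The concern.** A column headed placebo in an exposure table is normally read as time on placebo. Here, for any placebo-first subject who is retreated, it also carries all the time after Dysport. The Safety population is analysed by treatment actually received (SAP 5.3), and after the switch that treatment is not placebo. SAP 7.5 does not say whether its columns follow the first treatment or every treatment received.

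The exposure table also covers a different period from the adverse event tables. SAP 7.7.1 assigns each treatment-emergent event to the placebo-controlled cycle or to a Dysport cycle, cutting at the next administration. The exposure measure has no such cut. Someone reading placebo-cycle events beside placebo exposure would be comparing two different spans, and the placebo span could look as long as the Dysport span when the SAP itself expects the cycles to differ in length.

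**Working it through.** **Inputs**

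- Exposure formula: (last attended visit − first IMP date + 1)/7 (SAP 7.5).
- Earliest retreatment: more than 84 days after the previous IMP (SAP 2.2, Protocol 4.3). With placebo on Day 1, the first permitted day is Day 86, a gap of 85 days.
- End of study: Week 104, or 12 weeks after the last retreatment if that falls between Weeks 92 and 104 (SAP 2.2).
- Placebo-first subjects: 55 + 55 = 110 planned (SAP 2.2).
- Share of placebo subjects retreated, and when: not given. The switch days below are assumptions that show the range.

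**The plan's own figure.** The last permitted retreatment at Week 104 plus 12 weeks of follow-up is 116 weeks, and 104 − 12 = 92. Both agree with Protocol 3.4 and 5.2.7. The longest planned span the formula can cover is therefore (813 − 1 + 1)/7 = 116.1 weeks, where Week 116 is Day 1 + 7 × 116 = 813. The 104-week threshold is the top reporting category, not the maximum.

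**Placebo-first subject with end of study at Week 104**, which is Day 1 + 7 × 104 = 729:

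| First Dysport (assumed) | Weeks shown under placebo | Weeks before Dysport | Weeks by the Dysport formula | Share after Dysport |
|---|---|---|---|---|
| Day 86 | 729/7 = 104.1 | 85/7 = 12.1 | (729 − 86 + 1)/7 = 92.0 | 644/729 = 88% |
| Day 169 (Week 24) | 104.1 | 168/7 = 24.0 | 561/7 = 80.1 | 77% |
| Day 365 (Week 52) | 104.1 | 364/7 = 52.0 | 365/7 = 52.1 | 50% |
| Never | 104.1 | 104.1 | none | 0% |

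**Threshold counts.** The Day 86 subject is counted under placebo at all five thresholds (12, 24, 52, 78 and 104 weeks). On placebo-only time, 12.1 weeks, the subject belongs in the 12-week count alone.

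**Dysport-first subjects.** The first IMP date is also the first Dysport date, so the two formulas give the same value.

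**Check of the remedy.** If placebo time ends the day before first Dysport, the Day 86 subject has 85 days of placebo and 644 days of Dysport. These add to 729 days, the total, with no gap or overlap, and the boundary matches the one used for adverse events.

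**The case against.** The strongest defence is that the row does what its name says. Protocol 6.1 defines IMP as covering both active drug and placebo, so time from first IMP to last visit is a valid total-IMP figure when read by first treatment. Column titles and footnotes belong to a separate shell document (SAP 1), which is not available here and may clarify the heading. This stands in part: the number is not miscalculated. But a clearer label would not supply a placebo-only duration, and SAP 7.5 defines none.

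Four stronger readings are tempting, and the documents do not support them.

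- *That the placebo adverse event background will be reported as too low.* This would need events to be divided by this exposure. SAP 7.7.1 plans numbers and percentages of subjects and counts of occurrences, and SAP 7.1 bases percentages on subjects in the cycle. No person-time rate is planned. SAP 7.7.1 also repeats the overview and the system organ class and preferred term table for the first 12 weeks only. SAP 7.6.6.4 reports time between treatments for the placebo-controlled cycle by Kaplan-Meier methods.
- *That the table double-counts.* Post-switch weeks appear in both measures because Dysport time is nested within IMP time. Nothing in the SAP adds the two.
- *That every long placebo value is wrong, or that the whole group is overstated by some multiple.* A placebo subject never retreated does have about 104 weeks of placebo follow-up. The figures above describe single subjects, and the documents give no retreatment pattern from which to derive a group figure.
- *That the exposure data cited for ICH E1 are compromised.* Those concern Dysport exposure, and the Dysport formula starts at the first Dysport injection.

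**Conclusion.** The point holds as a labelling and completeness fault in one descriptive safety table. For each placebo-first subject who is retreated, the placebo column of SAP 7.5 includes time after Dysport. In the extreme assumed case (first Dysport on Day 86, end of study at Week 104) that is 92.0 of 104.1 weeks; with a switch at Week 52 it is about half. The number affected is however many of the planned 110 placebo subjects are retreated, which the documents do not state. No hypothesis test, alpha, power or planned adverse event percentage changes. It is still worth correcting, because the stated rule yields a placebo duration that readers will take at face value, and the summaries planned elsewhere mitigate this only in part.

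**What to change.** - Add a placebo (placebo-controlled cycle) exposure measure to SAP 7.5: (the earlier of the day before first Dysport and the last attended visit − first IMP date + 1)/7. Use it for the placebo duration and the placebo counts at 12 to 104 weeks.
- Keep the Total Dysport exposure formula and its counts as they are.
- If Total IMP exposure is retained for placebo-first subjects, head those columns by randomised sequence (placebo then 600 U, placebo then 800 U) instead of placebo. Simply truncating the placebo column of the existing row is not advised: one row would then have two definitions, and placebo-first subjects would lose their total-IMP figure.

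The cost is one extra row, with placebo exposure figures that come out shorter. All the dates needed are already used by the two existing formulas.

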7.6 Efficacy

The primary analysis based on the primary efficacy endpoint (mean change from study baseline in weekly number of UI episodes at Week 6 after the first IMP administration) will be performed on the mITT population.

The analysis for urodynamic parameters will be performed on the urodynamic population.

7.6.1 Significance Testing and Estimations

The primary efficacy hypotheses are as follows:

- 1) Ho: There is **no** difference between treatment with Dysport 600 U or Dysport 800 U and treatment with placebo with respect to the change from baseline to Week 6 after the first study treatment in the number of UI episodes per week.
- 2) Ha: There **is** a difference between treatment with Dysport 600 U or Dysport 800 U and treatment with placebo with respect to the change from baseline to Week 6 after the first study treatment in the number of UI episodes per week.

7.6.2 Multiplicity Adjustment

For the primary endpoint, due to multiple pairwise comparisons of each Dysport dose group versus placebo, a Hochberg correction will be applied to control the type one error at 5% significance level. The p-values from the two pairwise tests are ordered in magnitude from largest to smallest.

If both p-values for the two primary tests (the test of 600 U vs. placebo and the test of 800 U vs. placebo) are lower than 0.05, both will be declared statistically significant. If one of the primary tests has a p-value greater or equal to 0.05, then the other test will be declared

Statistical Analysis Plan

Version: Final v1.0

September-2018

Ipsen Protocol No. D-FR-52120-223

000000146513

Date of Issue: 21-

Covance Study ID:

statistically significant if its p-value is lower than 0.025 (and thus half of the overall experiment wise alpha of 0.05).

The two ordered secondary endpoints will be tested for both doses at the 0.05 level (using a hierarchical methodology) if, for both doses, the two primary tests achieve a p-value lower than 0.05. If one of the primary tests has a p-value greater or equal to 0.05, and the other has a p-value lower than 0.025, secondary endpoints will be assessed (using hierarchical methodology) for the dose group with p-value lower than 0.025, at the 0.025 significance level.

In order to control the family-wise type one error, the following hierarchical testing procedure will be applied for the testing of the superiority of both Dysport doses to placebo for the primary and selected secondary endpoints (ordered as described in Section 7.6.5):

- Step 1: The Dysport 600 U and Dysport 800 U will be compared to placebo on the primary endpoint. If the p-values associated with both doses are <0.05 then both doses will be declared statistically significant and the testing will proceed at the 0.05 level from step 2 onwards. If one dose has $p \geq 0.05$ but the other has $p < 0.025$ (significant dose) then testing will proceed at the 0.025 level from step 2 onwards on the significant dose only. If both dose groups have $p \geq 0.05$ or one dose group has $p \geq 0.05$ and the other dose group has $p \geq 0.025$, the testing procedure will be stopped.
- Step 2: The Dysport 600 U and Dysport 800 U will be compared to placebo for the first hierarchical secondary endpoint. Testing will be at the significance level defined in step 1 (0.05 or 0.025). If the p-value associated with this test is lower than the significance level defined in step 1 then it will be considered significant and testing will proceed to step 3. Otherwise the testing procedure will be stopped.
- Step 3: The Dysport 600 U and Dysport 800 U will be compared to placebo for the second hierarchical secondary endpoint. Testing will be at the significance level defined in step 2 (0.05 or 0.025). If the p-value associated with this test is lower than the significance level defined in step 2 then it will be considered significant.

The above testing rules ensure that the hierarchical procedure controls the experiment-wise type one error (i.e. over the three tests) at the 0.05 level for relevant secondary endpoints.

In the event the hierarchical testing procedure is stopped at the end of any particular step, the testing of the following steps will be considered descriptive only and no formal statistical conclusion will be drawn.

Each other secondary endpoint not included within the hierarchical testing procedure will be analysed for exploratory purposes only to compare each Dysport dose to placebo at a 0.05 type one error rate.

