#### 9.3 Significance Testing and Estimations

All statistical tests will be performed two-sided with a type one error rate set at 5%.

Experiment-wise control of type one error for the primary endpoint will be performed using a conservative approach. The primary efficacy hypotheses are as follows:

- (1) Ho: There is **no** difference between treatment with 600 U or 800 U Dysport® and treatment with placebo with respect to the change from pretreatment to Week 6 after the first study treatment in the number of UI episodes per week.
- (2) Ha: There **is** a difference between treatment with 600 U or 800 U Dysport® and treatment with placebo with respect to the change from pretreatment to Week 6 after the first study treatment in the number of UI episodes per week.

For the primary endpoint, due to multiple comparisons of more than two treatments, a Hochberg correction will be applied to control the global type one error at 5% significance level. If both p-values for the two primary tests (the test of 800 U vs. placebo and the test of 600 U vs. placebo) are lower than 0.05, both will be declared statistically significant. If one of the primary tests has a p-value greater or equal to 0.05, then the other test will be declared statistically significant if its p-value is lower than 0.025 (and thus half of the overall experiment wise alpha of 0.05).

The two ordered secondary endpoints will be tested for both doses at the 0.05 level (using a hierarchical methodology) if, for both doses, the two primary tests achieve a p-value lower than 0.05. If one of the primary tests has a p-value greater or equal to 0.05, and the other has a p-value lower than 0.025, secondary endpoints will be assessed (using hierarchical methodology) for the dose group with p-value lower than 0.025, at the 0.025 significance level.

In order to control the family-wise type one error, the following hierarchical testing procedure will be applied for the testing of the superiority of both Dysport® doses to placebo for the primary and selected secondary endpoints (ordered as described in Section 3.2.2.2):

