- Step 1: The 800 U Dysport® and 600 U Dysport® doses will be compared to placebo on the primary endpoint. If the p-values associated with both doses are <0.05 then both doses will be declared statistically significant and the testing will proceed at the 0.05 level from step 2 onwards. If one dose has  $p\ge0.05$  but the other has p<0.025 (significant dose) then testing will proceed at the 0.025 level from step 2 onwards on the significant dose only. If both dose groups have  $p\ge0.05$  or one dose group has  $p\ge0.05$  and the other dose group has  $p\ge0.025$ , the testing procedure will be stopped
- Step 2: The 800 U Dysport® and 600 U Dysport® doses will be compared to placebo for the first secondary endpoint. Testing will be at the significance level defined in step 1 (0.05 or 0.025). If the p-value associated with this test is lower than the significance level

PAGE 104/139

defined in step 1 then it will be considered significant and testing will proceed to step 3. Otherwise the testing procedure will be stopped

• Step 3: The 800 U Dysport® and 600 U Dysport® doses will be compared to placebo for the second secondary endpoint. Testing will be at the significance level defined in step 2 (0.05 or 0.025). If the p-value associated with this test is lower than the significance level defined in step 2 then it will be considered significant.

The above testing rules ensure that the hierarchical procedure controls the experiment-wise type one error (i.e. over the three tests) at the 0.05 level for relevant secondary endpoints.

In the event the hierarchical testing procedure is stopped at the end of any particular step, the testing of the following steps will be considered descriptive only and no formal statistical conclusion will be drawn.

Each other secondary endpoint not included within the hierarchical testing procedure will be analysed for exploratory purposes only to compare each Dysport® dose to placebo at a 0.05 type one error rate.

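### SAP 7.6.2 states 0.05 experiment-wise control for both doses on the primary and two key secondary endpoints, but its rules allow about 6 to 10%

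*SAP*

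**What the plan says.** SAP 7.6.2 introduces a three-step procedure to control the family-wise error "for the testing of the superiority of both Dysport doses to placebo for the primary and selected secondary endpoints". Two doses on three endpoints make six tests.

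- **Step 1, primary.** Hochberg across doses. Both are declared if both p-values are below 0.05; otherwise one dose can be declared at 0.025. The section describes that 0.025 as half of an experiment-wise 0.05.
- **Steps 2 and 3, continence then I-QoL.** If both doses won, both are tested at 0.05, with no further adjustment between them. If one dose won, "testing will proceed at the 0.025 level from step 2 onwards on the significant dose only".
- **Passing Step 2.** Two doses are compared, but the rule refers to one p-value: "If the p-value associated with this test is lower than the significance level defined in step 1 then it will be considered significant".
- **The claim.** "The above testing rules ensure that the hierarchical procedure controls the experiment-wise type one error (i.e. over the three tests) at the 0.05 level".

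Protocol 9.3 carries the same rules ("The two ordered secondary endpoints will be tested for both doses at the 0.05 level") and the same assurance ("The above testing rules ensure that the hierarchical procedure controls the experiment-wise").

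**The concern.** The doses are adjusted for each other at Step 1. After that, the only trace of the adjustment is the 0.025 carried forward when a single dose wins. This leaves two routes to excess error.

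1. **One dose wins.** When one dose clearly works, Hochberg tests the other on the primary at the full 0.05. If that dose is null, all of the 0.05 is spent on it. When it misses, the winner's secondaries are still tested at another 0.025.
2. **Both doses win.** Each dose is tested at 0.05 on each secondary, so there are two chances of a false claim at every step.

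The second route depends on how Step 2 is read, because the text does not say whether each dose is judged alone or both must pass. If one dose passes continence and the other does not, the SAP does not settle whether I-QoL is formally tested, or for which dose.

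Formal continence and I-QoL claims would rest on the 0.05 statement.

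**Working it through.** **Inputs from the documents**
- Two-sided tests at 5% (Protocol 9.3); thresholds of 0.05 and 0.025 as above (SAP 7.6.2).
- Arms of 110, 110 and 55 + 55 = 110 after pooling placebo (SAP 2.2). The two dose-placebo statistics share the placebo arm, so their correlation is (σ²/n)/(2σ²/n) = 0.5.
- Planned effect 21 − 12 = 9 episodes, SD 20, 96 per group (SAP 2.3). Noncentrality = 9/(20 × √(2/96)) = 3.12.

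**Assumed, because the documents do not give it:** correlation between endpoints, taken as 0 and 0.5.

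**The plan's own figure.** With all six nulls true, the simulated error is 4.8%. The 0.05 therefore holds for the primary endpoint and for the global null.

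**One dose effective on the primary and sure to pass; the other null; secondaries null.** With independent endpoints:

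0.05 + 0.95 × 0.025 = 0.0738

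Only one dose remains after Step 1 in this branch, so the reading of Step 2 makes no difference.

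**Both primaries sure to pass, continence null for both doses, each dose judged alone:**

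1 − P(|Z₁| < 1.96, |Z₂| < 1.96; ρ = 0.5) = 0.0907

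If both must be significant for any claim: 0.05 + 0.05 − 0.0907 = 0.0093.

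**Mixed case: continence real for one dose and null for the other, I-QoL null.** With both primaries and the real continence effect sure to pass, dose-by-dose gating and independent endpoints:

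1 − 0.95² = 0.0975

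**Simulation of the written rules**, 1,000,000 runs per scenario. Cells give the probability of at least one false claim (%) at between-endpoint correlation 0 / 0.5.

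| Scenario | Each dose alone, own gate | Each dose alone, Step 3 needs both | Both must win each step |
|---|---|---|---|
| All null | 4.8 / 4.8 | 4.8 / 4.8 | 4.8 / 4.8 |
| One dose effective, sure to pass | 7.4 / 7.3 | 7.4 / 7.3 | 7.4 / 7.3 |
| One dose effective, planned effect | 6.4 / 5.9 | 6.4 / 5.9 | 6.4 / 5.9 |
| Both primaries sure, secondaries null | 9.1 / 9.1 | 9.1 / 9.1 | 0.9 / 0.9 |
| Both primaries at planned effect, secondaries null | 7.5 / 6.4 | 7.5 / 6.4 | 1.1 / 0.8 |
| Mixed case | 9.7 / 9.6 | 5.0 / 5.0 | 5.0 / 5.0 |

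Using the 110 per arm to be randomised instead of 96, the fifth row becomes 8.0 / 7.0 when each dose is judged alone. A looser reading still, in which either dose passing Step 2 opens Step 3 for both, reaches 12 to 14% in the mixed case. Taken one at a time, each dose's own false-claim rate is at most 5.0% in these scenarios.

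**The case against.** The best defence is that three tests means one dose's chain of three endpoints, and that the sentence goes on to limit itself to the relevant secondary endpoints. Read that way it is true, since each dose's own rate stays at or below 5%. But the same section sets the family as both doses on all three endpoints, and halves alpha across doses at Step 1. If per-dose control is meant, the text has to say so.

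A second point is that most of the 7.4% is a false primary claim that Step 1 already allows. Counting only false secondary claims, the one-dose scenarios give at most about 3.4%. That is correct, but the stated family includes the primary.

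Third, the high figures are conditional. A joint gate at Step 2 is a fair reading, and it removes the excess when both doses win. The mixed-case 9.6 to 9.7% needs both primaries and one continence test to be certain. At the planned primary effect with 80% continence power it is 6.2 to 7.3% with dose-by-dose gating, and 3.6 to 4.3% if Step 3 needs both doses. All of this stands as a limit on size. It does not rescue the guarantee: strong control requires every configuration to be at or below 0.05, and the one-dose branch exceeds it under every reading.

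**Conclusion.** The concern holds. For the family the SAP defines, the 0.05 statement is wrong under every reading of Steps 2 and 3:

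- **Under any reading:** 7.3 to 7.4% when one dose is sure to pass and the other is null; 5.9 to 6.4% at the planned primary effect.
- **If each dose is judged alone:** 6.4 to 7.5% at the planned effect with null secondaries, 9.1% with assured primaries, and up to 9.7% in the mixed case with dose-by-dose gating.

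These are errors for particular scenarios, not one property of the plan, and some scenarios stay at or below 5%. They rest on a between-dose correlation of 0.5, which follows from the design, and an assumed between-endpoint correlation of 0 to 0.5. Primary-endpoint control is not affected. The urodynamic hierarchy in Protocol 9.6 is not counted, because SAP 7.6.6 treats endpoints outside the main hierarchy as exploratory.

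**What to change.** Choose one rule before unblinding and write it into SAP 7.6.2, Protocol 9.3 and the Protocol synopsis.

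- **Rule A.** Re-apply the Step 1 Hochberg rule across doses at Steps 2 and 3, continue only if both doses were significant at the current step, and make everything after Step 1 descriptive when one dose wins. Simulated error is at most about 5.0%. Repeating Hochberg while keeping the one-dose 0.025 branch is not enough; it still reaches 7.4%.
- **Rule B.** Run a separate primary, continence, I-QoL chain for each dose at 0.025. Simulated error is at most about 5.0%, and formal secondary claims survive when only one dose wins. A variant in which a completed chain passes its 0.025 to the other dose simulates at no more than 4.9% and recovers some power (planned effect: primary 83%, continence 62–68%, I-QoL 47–58%).

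At the least, say whether Step 2 judges each dose or both together, state which tests the 0.05 covers, and withdraw the claim of control across both doses.

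**Cost.** No new data. It needs a SAP amendment before database lock and a protocol amendment, which may count as substantial under Protocol 11.1.1. The power cost per dose, assuming 80% power for each secondary test at 0.05 and dose-by-dose gating as the starting point, is below. Ranges cover between-endpoint correlation 0 to 0.5.

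| | Primary | Continence | I-QoL |
|---|---|---|---|
| Current rules, primaries assured | – | 80% | 64–69% |
| Rule A, primaries assured | – | 77–78% | 53–58% |
| Current rules, planned effect | 86% | 68–72% | 54–63% |
| Rule A, planned effect | 86% | 62–66% | 42–52% |
| Rule B, planned effect | 81% | 58–63% | 41–53% |

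If the current text is instead read as needing both doses to open Step 3, Rule A's I-QoL loss with assured primaries is only about 1 to 2 points (55–60% to 53–58%). Rule A also gives up any formal secondary claim when a single dose wins.
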